### **Adverse events of special interest (AESIs)**

The term AESI relates to any specific AE that has been identified at the project level as being of particular concern for prospective safety monitoring and safety assessment within this trial, e.g. the potential for AEs based on knowledge from other compounds in the same class.

AESIs need to be reported to the sponsor's Pharmacovigilance Department within the same timeframe that applies to SAEs, please see above.

The following are considered as AESIs:

Hepatic injury

A hepatic injury is defined by the following alterations of hepatic laboratory parameters:

- an elevation of AST and/or ALT  $\geq 3$  fold ULN (upper limit of normal) combined with an elevation of total bilirubin  $\geq 2$  fold ULN measured in the same blood draw sample, and/or
- aminotransferase (ALT, and/or AST) elevations  $\geq 10$  fold ULN

These lab findings constitute a hepatic injury alert and the patients showing these lab abnormalities need to be followed up according to the "DILI checklist" which can be found in the EDC.

In case of clinical symptoms of hepatic injury (icterus, unexplained encephalopathy, unexplained coagulopathy, right upper quadrant abdominal pain, etc.) without lab results (ALT, AST, total bilirubin) available, the investigator should make sure these parameters are analysed, if necessary in an unscheduled blood test. Should the results meet the criteria of hepatic injury alert, the procedures described in the DILI checklist should be followed.

Intensity (severity) of AEs

The intensity (severity) of the AE should be judged based on the following:

- Mild: Awareness of sign(s) or symptom(s) that is/are easily tolerated  
Moderate: Sufficient discomfort to cause interference with usual activity  
Severe: Incapacitating or causing inability to work or to perform usual activities

Causal relationship of AEs

Medical judgement should be used to determine the relationship, considering all relevant factors, including pattern of reaction, temporal relationship, de-challenge or re-challenge, confounding factors such as concomitant medication, concomitant diseases and relevant history.

Arguments that may suggest that there is a reasonable possibility of a causal relationship could be:

- The event is consistent with the known pharmacology of the drug.
- The event is known to be caused by or attributed to the drug class.
- A plausible time to onset of the event relative to the time of drug exposure.
- Evidence that the event is reproducible when the drug is re-introduced
- No medically sound alternative aetiologies that could explain the event (e.g. pre-existing or concomitant diseases, or co-medications).
- The event is typically drug-related and infrequent in the general population not exposed to drugs (e.g. Stevens-Johnson syndrome).
- An indication of dose-response (i.e. greater effect size if the dose is increased, smaller effect size if dose is diminished).

Arguments that may suggest that there is no reasonable possibility of a causal relationship could be:

- No plausible time to onset of the event relative to the time of drug exposure is evident (e.g. pre-treatment cases, diagnosis of cancer or chronic disease within days / weeks of drug administration; an allergic reaction weeks after discontinuation of the drug concerned)
- Continuation of the event despite the withdrawal of the medication, taking into account the pharmacological properties of the compound (e.g. after 5 half-lives). Of note, this criterion may not be applicable to events whose time course is prolonged despite removing the original trigger.
- Additional arguments amongst those stated before, like alternative explanation (e.g. situations where other drugs or underlying diseases appear to provide a more likely explanation for the observed event than the drug concerned).
- Disappearance of the event even though the trial drug treatment continues or remains unchanged.

#### 5.2.6.2 Adverse event collection and reporting

##### AE Collection

Patients will be required to report spontaneously any AEs as well as the time of onset, duration and intensity of these events.

If patients report a change in perception or any vision-related AE, site staff must record the patient's verbatim description in the source documents to be reported in the eCRF (and SAE form if applicable). A local ophthalmology assessment will be required if any visual AE is rated as severe by the patient or at the discretion of the Principal Investigator. The ophthalmologist will act as a consultant to the investigator and may offer advice on the proper management and treatment for the reaction.

The potential for study drug abuse-related adverse events will be closely monitored and narratives provided in the Clinical Trial Report (CTR). Narratives will include standard AE data collection, including time of onset, duration, severity and outcome.

The investigator shall maintain and keep detailed records of all AEs in the patient files. The following must be collected and documented on the appropriate CRF(s) by the investigator:

- From signing the informed consent onwards until the individual patient's end of trial:
  - all AEs (serious and non-serious) and all AESIs.
- After the individual patient's end of trial:
  - the investigator does not need to actively monitor the patient for AEs but should only report related SAEs and related AESIs of which the investigator may become aware of by any means of communication, e.g. phone call. Those AEs should however, not be reported in the CRF.

[figure not shown]

Figure 5.2.6.2: 1 AE Collection

Patients who discontinue trial medication prematurely and agree to be contacted further, should be followed up as described in [Section 3.3.4.1](#), withdrawal from trial treatment. From then on until the individual patient's end of the trial the investigator must report:

- All AEs/SAEs/AESIs collected by the investigator as instructed in [Section 3.3.4.1](#) for patients who choose Options 1 and 2.
- All AEs/SAEs/AESIs the investigator becomes aware of for patients who choose Options 3 and 4.

After the individual patient's end of the trial the investigator does not need to actively monitor the patient for AEs but should report related SAEs and related AESIs of which the investigator may become aware of by any means of communication, e.g. phone call. Those AEs should however, not be reported in the CRF.

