### 7.3 PLANNED ANALYSES

Two patient populations are defined:

- The treated set (TS) includes all patients who were dispensed study medication and were documented to have taken at least one dose of investigational treatment
- The full analysis set (FAS) includes all patients in the treated set with at least one post-baseline measurement of any type

No per protocol population will be used for analyses; however protocol violations will be identified and listed.

Analysis sets will be fully defined in TSAP.

Three analysis periods are defined:

- **Intent to Treat (ITT) follow-up:** from treatment start date until the end of the intended complete treatment period:

For patients who complete the trial according to the [flow chart](#), the withdrawal/taper period is not included. Additionally, if a patient happens to take drug for 29 weeks (i.e. 1 week longer than the planned 28 weeks) and then begin the withdrawal/taper period, the withdrawal/taper period will not be included.

For patients who discontinue prior to the 28 week treatment period, e.g. at week 25, the follow-up period until the end of week 28, is included.

- **Full follow-up:** from randomisation until the end of the trial, including all observed time on and off trial medication until the follow-up visit or the last date of contact:

For patients who discontinue trial medication according to the [flow chart](#), the withdrawal/taper period is included. Additionally, if a patient happens to take drug for 29 weeks (i.e. 1 week longer than the planned 28 weeks) and then begin the withdrawal/taper period, the withdrawal/taper period is included.

For patients who discontinue prior to the 28 week treatment period, e.g. at week 25, the follow-up period until the last contact date is included.

The full follow-up analysis period will be used as a sensitivity analysis to the ITT follow-up analysis.

- **On-treatment:** from treatment start date until the date of discontinuation of trial medication + 7 days:

For all patients this analysis period includes only the time on trial medication + 7 days after taken off trial medication.

For patients randomised to the withdrawal period, this will include 28 weeks of treatment, or for early discontinued patients, the time period on active treatment prior to discontinuation + 7 days, which corresponds to the 7 days abrupt withdrawal period.

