For patients randomised to the taper period, this will include 28 weeks of treatment + the tapering period (of 7 days) + 7 days, or for early discontinued patients, simply the time period on randomised active treatment prior to discontinuation + 7 days (because tapering will not be done for patients discontinued early).

The on-treatment analysis period will be used to analyse safety.

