### **7.3.4 Safety analyses**

Adverse events will be coded using the Medical Dictionary for Regulatory Activities (MedDRA). Standard BI summary tables and listings will be produced. All adverse events with an onset between start of treatment and end of the residual effect period (REP), a period of 7 days after the last dose of trial medication, will be assigned to the on-treatment period (see above) for evaluation.

All treated patients will be included in the safety analysis. In general, safety analyses will be descriptive in nature and will be based on BI standards. No hypothesis testing is planned.

Statistical analysis and reporting of adverse events will concentrate on treatment-emergent adverse events, i.e. all adverse events occurring between start of treatment and end of the

residual effect period. Adverse events that start before first drug intake and deteriorate under treatment will also be considered as ‘treatment-emergent’.

Frequency, severity, and causal relationship of adverse events will be tabulated by system organ class and preferred term after coding according to the current version of MedDRA at the database lock.

Laboratory data will be analysed both quantitatively as well as qualitatively. The latter will be done via comparison of laboratory data to their reference ranges. Values outside the reference range as well as values defined as clinically relevant will be summarised. Treatment groups will be compared descriptively with regard to distribution parameters as well as with regard to frequency and percentage of patients with abnormal values or clinically relevant abnormal values.

Vital signs, physical examinations, or other safety-relevant data observed at screening, baseline, during the course of the trial and at the end-of-trial evaluation will be assessed with regard to possible changes compared to findings before start of treatment.

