7.8.1 Adverse events

Unless otherwise specified, the analyses of adverse events will be descriptive in nature. All analyses of AEs will be based on the number of subjects with AEs and NOT on the number of AEs.

For analysis multiple AE occurrence data on the CRF will be collapsed into an AE provided that all of the following applies:

- All AE attributes are identical (LLT, intensity, action taken, therapy required, seriousness, reason for seriousness, relationship, outcome, AE of special interest)
- The occurrences were time-overlapping or time-adjacent (time-adjacency of 2 occurrences is given if the second occurrence started on the same day or on the day after the end of the first occurrence).

For further details on summarization of AE data, please refer to (3, 4).

The analysis of adverse events will be based on the concept of treatment emergent adverse events. That means that all adverse events occurring between first drug intake till last drug intake + residual effect period will be assigned to the randomised treatment. All adverse events occurring before first drug intake will be assigned to 'screening' and all adverse events occurring after the residual effect period will be assigned to 'post-treatment' (for listings only). For details on the treatment definition, see Section 6.1.

According to ICH E3 (5), AEs classified as 'other significant' need to be reported and will include those non-serious and non-significant adverse events with:

(i) 'action taken = discontinuation' or 'action taken = reduced', or

Proprietary confidential information © 2021 Boehringer Ingelheim International GmbH or one or more of its affiliated companies

(ii) marked haematological and other lab abnormalities or lead to significant concomitant therapy as identified by the Clinical Monitor/Investigator at a Medical Quality Review Meeting.

An overall summary of adverse events will be presented.

The frequency of subjects with adverse events will be summarized by treatment, primary system organ class and preferred term. Separate tables will be provided for subjects with other significant adverse events according to ICH E3 (5), for subjects with adverse events of special interest (detailed in section 5.2.6.1 of the revised CTP) and for subjects with serious adverse events.

The system organ classes will be sorted alphabetically, preferred terms will be sorted by frequency (within system organ class).

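### SAEs and deaths starting more than 7 days after the last dose are collected but appear in no by-arm safety table in the plan

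*Protocol*

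**What the plan says.** **Collection.** Under AE Collection in protocol section 5.2.6.2, once a patient has stopped drug early, "From then on until the individual patient's end of the trial the investigator must report" all AEs, SAEs and AESIs. For Options 1 and 2 they are collected actively. For Options 3 and 4 the duty is limited to "All AEs/SAEs/AESIs the investigator becomes aware of for patients who choose Options 3 and 4".

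**Overlap with relapse.** Several relapse criteria are also (S)AE records. Section 5.2.6.2 (Information required) has worsening of the underlying disease recorded as an (S)AE. Inpatient hospitalisation is an SAE criterion in section 5.2.6.1. Section 5.2.5.1 makes type 4 or 5 ideation and suicidal behaviour separate SAEs. SAP section 6.6 itself refers to AEs that satisfy the primary endpoint criteria.

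**Efficacy window.** The primary analysis uses ITT follow-up. Protocol section 7.3 states: "For patients who discontinue prior to the 28 week treatment period, e.g. at week 25, the follow-up period until the end of week 28, is" part of that analysis period.

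**Safety window.** Protocol section 7.3 states "The on-treatment analysis period will be used to analyse safety". Section 7.3.4 defines the residual effect period as "a period of 7 days after the last dose of trial medication" and says "Statistical analysis and reporting of adverse events will concentrate on treatment-emergent adverse events". SAP section 7.8.1 then states that "all adverse events occurring after the residual effect period will be assigned to 'post-treatment' (for listings only").

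**The concern.** The two windows part for anyone who stops drug early. Relapse is followed to week 28 whether or not the patient is on drug, while adverse events are tabulated only to last dose plus 7 days. A hospitalisation for psychosis some weeks after stopping can be a primary-endpoint event and an SAE, yet be missing from the SAE table. A non-relapse SAE or a death from another cause at the same time point is in a listing and in no arm comparison at all.

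At stake is whether a between-arm difference in late SAEs or deaths can be seen without counting through listings. This matters more than usual here. Protocol section 1.4 says an effect on suicidality cannot be ruled out, and the rationale in section 1.3 rests partly on an SAE imbalance in an earlier trial of this drug.

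**Working it through.** **1. Setting the windows side by side.** Take a patient whose last dose is on day 60 and who is hospitalised for psychosis on day 120.
- ITT follow-up runs to Visit 16, about day 197. Day 120 is inside it, so this is a primary-endpoint event.
- The on-treatment period ends on day 60 + 7 = 67. Day 120 is outside it, so the SAE is post-treatment and listed only.
- The untabulated part of ITT follow-up is day 68 to about day 197, that is 197 − 67 = 130 days.

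**2. Looking for another table that fills the gap.** The AE, SAE and AESI tables in SAP section 7.8.1 all rest on the treatment-emergent concept. The withdrawal/taper analysis (protocol section 7.3.4, SAP section 7.8.5) uses only data from that 7-day period after week 28. Neither document specifies an AE, SAE or death table over ITT or full follow-up.

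**3. The plan's own figure (background).** For HR 0.50, 2:1 allocation, two-sided 0.05 and 80% power, required events = (1.960 + 0.842)² / [(1/3)(2/3)(ln 0.5)²] = 73.5, so 74, as protocol section 7.7 states. The point does not depend on this figure.

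**4. Illustrative size.** Inputs from section 7.7: placebo relapse 30%, HR 0.50, 129 placebo and 258 active. Assumptions that are not in the documents: a constant drug-discontinuation hazard reaching 20% or 40% by week 28, and every discontinuer followed to week 28.

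*Patient-time.* With d = −ln(1 − q)/28 per week, mean time later than 7 days after stopping and before week 28 is 27 − (1 − e^(−27d))/d. Planned time is 387 × 28 = 10,836 patient-weeks.
- q = 20%: 2.71 weeks per patient, × 387 = about 1,048 patient-weeks, 9.7%.
- q = 40%: 5.68 weeks per patient, × 387 = about 2,198 patient-weeks, 20.3%.

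*Relapses.* Total with full follow-up = 129 × 0.30 + 258 × (1 − √0.7) = 38.7 + 42.1 = 80.8. With 28 weeks as the time unit, δ = −ln(1 − q), g = 7/196, on-drug hazard λ and off-drug hazard μ, the chance of a first relapse in the gap is ∫ from 0 to 1 − g of δ e^(−(δ+λ)t) e^(−μg) [1 − e^(−μ(1−t−g))] dt. Here λ = 0.357 for placebo and 0.178 for active. Two cases are shown: μ = λ, and μ = 0.357 in the active arms (benefit lost on stopping).

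| Stop early | Case | Placebo | Active | Total, of about 81 |
|---|---|---|---|---|
| 20% | hazard unchanged | 3.5 | 3.9 | 7.5 |
| 40% | hazard unchanged | 7.4 | 8.3 | 15.7 |
| 20% | benefit lost | 3.5 | 7.4 | 10.9 |
| 40% | benefit lost | 7.4 | 15.6 | 22.9 |

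The total of 81 is held at the plan's rates; it would itself rise somewhat if benefit were lost. Multiplying the average hazard by all the off-drug time gives 8.9 and 18.7, which is too high because that time includes patients who had already relapsed.

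**The case against.** Last dose plus a residual effect period is a common convention, and no two passages contradict each other. Both points stand: this is an omission, and the convention should stay for the main tables. Three stronger readings are tempting, and the documents do not support them.

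- *Relapses in the primary analysis appear in no safety table.* This is too broad. Relapses recorded as AEs on drug or within 7 days of the last dose are treatment-emergent and are tabulated.
- *Benefit is counted over all time and harm only on drug.* Off-drug relapses, which include hospitalisation for decompensation and suicidal behaviour, are harms and are compared by randomised arm. They enter the primary Cox analysis, the Full follow-up sensitivity analysis and the composite of discontinuation or relapse (SAP sections 7.4.1 and 7.4.2). Off-drug C-SSRS events may also enter the relative-risk output of SAP section 7.5.2, for which protocol section 7.5 keeps all FAS patients regardless of dropout. These are efficacy outputs, though, and they do not show non-relapse SAEs or deaths.
- *The abrupt stop of early discontinuers goes unexamined.* They are not tapered ("because tapering will not be done for patients discontinued early"), but protocol section 7.3 includes their 7 days after stopping and equates those days with the abrupt withdrawal period. The gap starts on day 8.

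A further objection is that AE summarisation is referred to sponsor standards that are not available here, and that concentrating on treatment-emergent events is not the same as reporting only those. A standard table may exist. The plan as written says listings only; naming such a table in the SAP would settle the point.

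The size is also open to challenge. The 20% in section 7.7 is dropout in a sample-size calculation; treated as censoring it yields about 73 events, close to the 74 required. It is not a drug-discontinuation rate with full follow-up. Section 7.3.1 also assumes no relapse where one cannot be determined after discontinuation. The counts are therefore an illustration and not a forecast.

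**Conclusion.** The point holds as an omission. SAEs and deaths that start later than last dose plus 7 days are collected but have no by-arm safety table in either document. What is left without any arm comparison is chiefly non-relapse SAEs and non-relapse deaths; late relapses are compared as efficacy events but are absent from the SAE tables.

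The illustrated 9.7% to 20.3% of patient-time and 7 to 16 relapses (11 to 23 if benefit is lost) rest on assumed discontinuation of 20% to 40%, complete follow-up and 387 patients. SAP section 4 says recruitment stopped early, so counts would be lower at any given rate, although the proportions would not change. The existence of the gap follows from the definitions of the windows and needs none of these figures.

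**What to change.** Keep the on-treatment tables as the main safety analysis. Add to SAP section 7.8.1 one supplementary table of SAEs (including suicidality SAEs) and deaths by randomised arm over the ITT follow-up period. It should show observed patient-time for each arm and carry a note that capture is passive for Options 3 and 4. State the randomised-arm rule explicitly, because SAP section 6.3 assigns safety data by the treatment received when the AE occurred, which gives no clear group for an event off drug.

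A separate summary restricted to early discontinuers is not needed. If shown, it should be labelled descriptive, because that group is selected after randomisation and a difference between arms within it is not a randomised comparison.

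The cost is one extra table on data already collected, with no change to conduct, endpoints or alpha. The downside is less complete capture for Options 3 and 4, which is why the table is limited to SAEs and deaths.

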### AE reporting to sponsor and timelines

The investigator must report SAEs, AESIs, and non-serious AEs which are relevant for the reported SAE or AESI, on the BI SAE form via fax immediately (within 24 hours ) to the sponsor's unique entry point (country specific contact details will be provided in the ISF). The same timeline applies if follow-up information becomes available. In specific occasions the investigator could inform the sponsor upfront via telephone. This does not replace the requirement to complete and fax the BI SAE form.

With receipt of any further information to these events, a follow-up SAE form has to be provided. For follow-up information the same rules and timeline apply as for initial information.

### Information required

For each AE, the investigator should provide the information requested on the appropriate eCRF pages and the BI SAE form, if applicable. The investigator should determine the causal relationship to the trial medication.

The following should also be recorded as an (S)AE in the CRF and BI SAE form (if applicable):

- Worsening of the underlying disease or of other pre-existing conditions
- Changes in vital signs, ECG, physical examination and laboratory test results, if they are judged clinically relevant by the investigator.

If such abnormalities already pre-exist prior to trial inclusion they will be considered as baseline conditions and should be collected in the eCRF only. All (S)AEs, including those persisting after individual patient's end of trial must be followed up until they have resolved, have been assessed as "chronic" or "stable", or no further information can be obtained.

